### 7.2. Participant Discontinuation/Withdrawal from the Study

- A participant may withdraw from the study at any time at his/her own request, or may be withdrawn at any time at the discretion of the investigator for safety, behavioral, compliance, or administrative reasons. This is expected to be uncommon.
- At the time of discontinuing from the study, if possible, an early discontinuation visit should be conducted, as shown in the SoA. See SoA for data to be collected at the time of study discontinuation and follow-up and for any further evaluations that need to be completed.
- The participant will be permanently discontinued both from the study intervention and from the study at that time.
- If the participant withdraws consent for disclosure of future information, the sponsor may retain and continue to use any data collected before such a withdrawal of consent.
- If a participant withdraws from the study, he/she may request destruction of any samples taken and not tested, and the investigator must document this in the site study records.

### 7.3. Lost to Follow up

A participant will be considered lost to follow-up if he or she repeatedly fails to return for scheduled visits and is unable to be contacted by the study site.

The following actions must be taken if a participant fails to return to the clinic for a required study visit:

- The site must attempt to contact the participant and reschedule the missed visit as soon as possible and counsel the participant on the importance of maintaining the assigned visit schedule and ascertain whether or not the participant wishes to and/or should continue in the study.

This document, including any source code, is the property of [Clinvest Research LLC](#), and may contain proprietary, confidential, or legally privileged information. No part of this report, or any information contained therein, may be disseminated without the written consent of [Clinvest Research LLC](#).

- Before a participant is deemed lost to follow up, the investigator or designee must make every effort to regain contact with the participant (where possible, 3 telephone calls and, if necessary, a certified letter to the participant's last known mailing address or local equivalent methods). These contact attempts should be documented in the participant's medical record.
- Should the participant continue to be unreachable, he/she will be considered to have withdrawn from the study.

Discontinuation of specific sites or of the study as a whole are handled as part of Appendix 1.

This document, including any source code, is the property of [Clinvest Research LLC](#), and may contain proprietary, confidential, or legally privileged information. No part of this report, or any information contained therein, may be disseminated without the written consent of [Clinvest Research LLC](#).

## **8. Study Assessments and Procedures**

- Study procedures and their timing are summarized in the SoA. Protocol waivers or exemptions are not allowed.
- Immediate safety concerns should be discussed with the sponsor immediately upon occurrence or awareness to determine if the participant should continue or discontinue study intervention.
- Adherence to the study design requirements, including those specified in the SoA, is essential and required for study conduct.
- All screening evaluations must be completed and reviewed to confirm that potential participants meet all eligibility criteria. The investigator will maintain a screening log to record details of all participants screened and to confirm eligibility or record reasons for screening failure, as applicable.

### **8.1. Efficacy Assessments**

#### **8.1.1. Migraine Interictal Burden Scale (MIBS-4)**

Participants will complete an electronic version of the MIBS-4 within the clinic during visits outlined in the SoA.

#### **8.1.2. Migraine Days via Daily Headache Diary (DHD)**

Headache and Migraine data will be recorded by the participants into an electronic daily headache diary (DHD) throughout the study. The DHDs are web-based and can be completed on any internet enabled device. Participants will be given their unique DHD URL at Visit 1. Site personnel will be responsible for instructing participants on the requirement for timely and daily completion of the DHD. Participants will be asked to record diary data each day for the previous day (24-hour period). If a participant does not experience a headache in the previous 24-hour period, the diary must still be completed as instructed. Participant's diaries may vary day to day based on their responses. All participants should have at least 80% compliance with diary completion throughout the length of the study. Participants will record headache severity, symptoms, use of acute medications, as well as additional assessments as required.

#### **8.1.3. Neuro-QoL Sleep Disturbance Short Form (SDSF)**

Participants will complete an electronic version of the SDSF within the clinic during visits outlined in the SoA.

**8.1.4. General Self-Efficacy Short Form (GSE-SF)**

Participants will complete an electronic version of the GSESS within the clinic during visits outlined in the SoA.

**8.1.5. PROMIS-29**

Participants will complete an electronic version of the PROMIS-29 within the clinic during visits outlined in the SoA.

**8.1.6. Work Productivity and Activity Impairment- Migraine (WPAI-M)**

Participants will complete an electronic version of the WPAI-M within the clinic during visits outlined in the SoA.

**8.1.7. Brief Measure of Worry Severity (BMWS)**

Participants will complete an electronic version of the BMWS within the clinic during visits outlined in the SoA.

**8.1.8. Activity and Sleep via wearable device**

Participants' activity and sleep data will be recorded via a sponsor-provided wearable device (e.g., Fitbit or similar). Participants may also be required to install the wearable device's phone application on their personal phones in order for the data to be transferred to the sponsor. Site personnel will be responsible for instructing participants on the requirement(s) of the wearable device and its associated phone application if applicable.

**8.2. Safety Assessments**

Planned time points for all safety assessments are provided in the SoA.

**8.2.1. Physical and Neurological Examinations**

- A complete physical examination will include, at a minimum, assessments of the Cardiovascular, Respiratory, and Gastrointestinal systems. Height and weight will also be measured and recorded.
- A complete neurological examination will be performed.
- Investigators should pay special attention to clinical signs related to previous serious illnesses.

**8.2.2. Vital Signs**

- Oral temperature, pulse rate, respiratory rate, and blood pressure will be assessed.
- Blood pressure and pulse measurements will be assessed.

- Blood pressure and pulse measurements should be preceded by at least 5 minutes of rest for the participant in a quiet setting without distractions (e.g., television, cell phones).
- Vital signs will be measured in a semi-supine position after 5 minutes rest and will include temperature, systolic and diastolic blood pressure, and pulse.

#### **8.2.3.     Electrocardiograms**

- 12-lead ECG's will be obtained as outlined in the SoA (see Section 1.3). The heart rate, PR, QRS, QT, and QTc intervals will be measured/calculated. Investigators will read final EKG's and determine any abnormalities. The overall interpretation and determination of the clinical relevance of ECG findings will be the responsibility of the investigator

#### **8.2.4.     Clinical Safety Laboratory Assessments**

- See Appendix 2 for the list of clinical laboratory tests to be performed and to the SoA for the timing and frequency.
- The investigator must review the laboratory report, document this review, and record any clinically relevant changes occurring during the study in the AE section of the CRF. The laboratory reports must be filed with the source documents. Clinically significant abnormal laboratory findings are those which are not associated with the underlying disease, unless judged by the investigator to be more severe than expected for the participant's condition.
- All laboratory tests with values considered clinically significantly abnormal during participation in the study should be repeated until the values return to normal or baseline or are no longer considered clinically significant by the investigator or medical monitor.
  - If such values do not return to normal/baseline within a period of time judged reasonable by the investigator, the etiology should be identified and Clinvest and the medical monitor notified.
  - All protocol-required laboratory assessments, as defined in Appendix 2, must be conducted in accordance with the SoA.
  - If laboratory values from non-protocol specified laboratory assessments performed at the institution's local laboratory require a change in participant management or are considered clinically significant by the investigator (e.g., SAE or AE or dose modification), then the results must be recorded in the CRF.

### **8.2.5. Suicidal Ideation and Behavior Risk Monitoring**

Participants being treated with fremanezumab-vfrm should be monitored appropriately and observed closely for suicidal ideation and behavior or any other unusual changes in behavior, especially at the beginning and end of the course of intervention, or at the time of dose changes, either increases or decreases. Consideration should be given to discontinuing the study medication in participants who experience signs of suicidal ideation or behavior, following a risk assessment.

Baseline assessment of suicidal ideation and behavior/ intervention emergent suicidal ideation and behavior will be monitored during the study using PHQ-9.

## **8.3. Adverse Events and Serious Adverse Events**

AEs will be reported by the participant (or, when appropriate, by a caregiver, surrogate, or the participant's legally authorized representative).

The investigator and any qualified designees are responsible for detecting, documenting, and recording events that meet the definition of an AE or SAE and remain responsible for following up AEs that are serious, considered related to the study intervention or study procedures, or that caused the participant to discontinue the study intervention or study (see Section 7).

### **8.3.1. Time Period and Frequency for Collecting AE and SAE Information**

All SAEs will be collected from the signing of the informed consent form (ICF) until Visit 5 as specified in the SoA (Section 1.3).

All AEs will be collected from the start of intervention until Visit 5 as specified in the SoA (Section 1.3).

Medical occurrences that begin before the start of study intervention but after obtaining informed consent will be recorded on the Medical History/Current Medical Conditions section of the CRF not the AE section.

All SAEs will be recorded and reported to the sponsor or designee immediately and under no circumstance should this exceed 24 hours, as indicated in Appendix 3. The investigator will submit any updated SAE data to the sponsor within 24 hours of it being available.

Investigators are not obligated to actively solicit reports of AE's or SAE's after conclusion of the study participation. However, if the investigator learns of any SAE, including a death, within five half-lives after a participant has been discharged from the study, and he/she considers the event to be reasonably related to the study intervention or study participation, the investigator must promptly notify the sponsor.

### **8.3.2. Method of Detecting AEs and SAEs**

The method of recording, evaluating, and assessing causality of AE and SAE and the procedures for completing and transmitting SAE reports are provided in Appendix 10.3.

Care will be taken not to introduce bias when detecting AEs and/or SAEs. Open-ended and non-leading verbal questioning of the participant is the preferred method to inquire about AE occurrences.

### **8.3.3. Follow-up of AEs and SAEs**

After the initial AE/SAE report, the investigator is required to proactively follow each participant at subsequent visits/contacts. All SAEs, and AEs will be followed until resolution, stabilization, the event is otherwise explained, or the participant is lost to follow-up (as defined in Section 7.3). Further information on follow-up procedures is provided in Appendix 10.3.

### **8.3.4. Regulatory Reporting Requirements for SAEs**

- Prompt notification by the investigator to the sponsor of a SAE is essential so that legal obligations and ethical responsibilities towards the safety of participants and the safety of a study intervention under clinical investigation are met.
- The sponsor has a legal responsibility to notify both the local regulatory authority and other regulatory agencies about the safety of a study intervention under clinical investigation. The sponsor will comply with country-specific regulatory requirements relating to safety reporting to the regulatory authority, Institutional Review Boards (IRB)/Independent Ethics Committees (IEC), and investigators.
- For all studies except those utilizing medical devices investigator safety reports must be prepared for suspected unexpected serious adverse reactions (SUSAR) according to local regulatory requirements and sponsor policy and forwarded to investigators as necessary.
- An investigator who receives an investigator safety report describing a SAE or other specific safety information (e.g., summary or listing of SAEs) from the sponsor will review and then file it along with the Investigator's Brochure and will notify the IRB/IEC, if appropriate according to local requirements.

### **8.3.5. Pregnancy**

- Details of all pregnancies in female participants and, female partners of male participants will be collected after the start of study intervention and until 5 terminal half-lives after the last dose. Pregnancies will be followed until delivery.

- If a pregnancy is reported, the investigator should inform the sponsor within 24 hours of learning of the pregnancy and should follow the procedures outlined in Appendix 10.4.
- Abnormal pregnancy outcomes (e.g., spontaneous abortion, fetal death, stillbirth, congenital anomalies, ectopic pregnancy) are considered SAEs.

#### **8.4. Treatment of Overdose**

Not applicable, all treatments will be delivered in clinic by investigator or designee.

#### **8.5. Pharmacokinetics**

Not applicable, pharmacokinetic parameters are not evaluated in this study.

#### **8.6. Genetics**

Not applicable, genetics are not evaluated in this study.

#### **8.7. Biomarkers**

Not applicable, biomarkers are not evaluated in this study.

#### **8.8. Immunogenicity Assessments**

Not applicable, immunology assessments are not evaluated in this study.

#### **8.9. Medical Resource Utilization and Health Economics**

Not applicable, medical resource utilization and health economics are not evaluated in this study.

## 9. Statistical Considerations

### 9.1. Statistical Hypotheses

The null hypothesis of this study is that participants' global Migraine Interictal Burden Scale (MIBS-4) scores will not be statistically different between 50% responders and non-responders from baseline (Visit 2) to any 4-week treatment period during the 12-week treatment period after 3 months dose of 225 mg fremanezumab-vfrm.

### 9.2. Sample Size Determination

To determine the needed sample size for this study we utilized G\*Power Version 3.1.9.3 to conduct a power analysis for the Primary Endpoint analysis (repeated measures ANOVA, within-between interaction) comparing baseline MIBS-4 scores to treatment month(s) MIBS-4 scores between 50% responders and non-responders. Based on prior research, we expect an approximate equal proportion of responders and non-responders in this open-label study. The power analysis indicated that a total of 36 subjects would be adequate to detect a medium effect ( $f= 0.25$ ), with alpha set at 0.05, and a power of .95. To account for a 10% early withdrawal rate, a total of 40 subjects should be enrolled in the study.

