### Number of Participants:

A maximum of 40 participants will be enrolled to study intervention.

**Note:** "Enrolled" means a participant's, or their legally acceptable representative's, agreement to participate in the clinical study following completion of the informed consent process and the 4-week run-in period. Potential participants who are screened for the purpose of determining eligibility for the study, but do not participate in the study via at least one administration of IP, are not considered enrolled.

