### 3. Objectives and Endpoints

Objectives	Endpoints

Primary
 
1. To evaluate the efficacy of fremanezumab-vfrm on interictal migraine related burden between 50% responders and non-responders, via change in Migraine Interictal Burden Scale (MIBS-4) score during the 12-week treatment phase.
	
1. Change in monthly Migraine Interictal Burden Scale (MIBS-4) scores from baseline to each 4-week treatment period during the 12-week treatment period comparing between 50% responders and non-responders within subjects treated with fremanezumab-vfrm.

Secondary
 
To evaluate the efficacy of fremanezumab-vfrm between 50% responders and non-responders on the following parameters during the 12-week treatment phase:
 
1. Change in migraine days  2. Change in Neuro-QoL Sleep Disturbance Short Form (SDSF)  3. Change in General Self-Efficacy Short Form (GSE-SF)  4. Change in PROMIS-29  5. Change in Work Productivity and Activity Impairment- Migraine (WPAI-M)  6. Change in Brief Measure of Worry Severity (BMWS)  7. To evaluate the safety and tolerability of subjects treated with fremanezumab-vfrm
	
Change from baseline to each 4-week treatment period during the 12-week treatment period comparing between 50% responders and non-responders within subjects treated with fremanezumab-vfrm on the following:
 
1. Number of migraine days  2. Neuro-QoL Sleep Disturbance Short Form (SDSF) scores  3. General Self-Efficacy Short Form (GSE-SF) scores  4. PROMIS 29 scores  5. Work Productivity and Activity Impairment- Migraine (WPAI-M) scores  6. Brief Measure of Worry Severity (BMWS) scores  7. Safety and tolerability of fremanezumab-vfrm in study participants via collection of adverse events and safety evaluations.

This document, including any source code, is the property of [Clinvest Research LLC](#), and may contain proprietary, confidential, or legally privileged information. No part of this report, or any information contained therein, may be disseminated without the written consent of [Clinvest Research LLC](#).

Objectives	Endpoints

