### 9.4. Statistical Analyses

The statistical analysis plan (SAP) will be finalized prior to database lock and it will include a more technical and detailed description of the statistical analyses described in this section. This section is a summary of the planned statistical analyses of the most important endpoints including primary and key secondary endpoints. In case of a discrepancy, the SAP will supersede the protocol.

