#### **9.4.1. General considerations**

An alpha of .05 will be used for statistical significance for all statistical tests. All statistically significant multivariate analyses will be followed by univariate post-hoc tests. Appropriate multiple comparison adjustments will be made if needed. A Last Observation Carried Forward (LOCF) method will be utilized to impute missing data where appropriate.

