#### **9.4.2. Primary endpoint**

Data for the primary endpoint will be statistically analyzed via a repeated measures ANOVA, within-between interaction comparing baseline MIBS-4 scores to treatment month(s) MIBS-4 scores between 50% responders and non-responders.

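### Does calling f = 0.25 a medium effect in Section 9.2 overstate what 36 participants can show on MIBS-4?

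*Combined protocol and SAP*

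**What the plan says.** Section 9.2 sizes the study on the within-between interaction of a repeated measures ANOVA, with responders and non-responders expected in about equal numbers. It reports: "The power analysis indicated that a total of 36 subjects would be adequate to detect a medium effect". The effect is given as f = 0.25, with alpha 0.05 and power 0.95, and a 10% withdrawal allowance raises 36 to 40. The synopsis sets the ceiling: "A maximum of 40 participants will be enrolled to study intervention". Section 9.4.2 plans the test that was powered, a "repeated measures ANOVA, within-between interaction comparing baseline MIBS-4 scores to treatment month(s) MIBS-4 scores".

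Section 9.2 does not give the number of visits, the correlation between them, the sphericity assumption or the effect-size option. It gives no MIBS-4 SD and no difference in points.

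The time frame of the claim is worded in several ways. The primary endpoint in Section 3 is "Change in monthly Migraine Interictal Burden Scale (MIBS-4) scores from baseline to each 4-week treatment period", while the null hypothesis in Section 9.1 runs from baseline "to any 4-week treatment period during the 12-week treatment period after 3 months dose". On follow-up tests, Section 9.4.1 says: "All statistically significant multivariate analyses will be followed by univariate post-hoc tests" and "Appropriate multiple comparison adjustments will be made if needed". Section 9.4 leaves technical detail to a later document: "The statistical analysis plan (SAP) will be finalized prior to database lock".

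**The concern.** With two equal groups and one measurement, f is half the standardised difference, so f = 0.25 is 0.5 SD. A reader with that yardstick would take Section 9.2 to promise a 95% chance of detecting a half-SD difference between responders and non-responders. The interaction test spreads f over all visits, including a baseline at which the gap in change is zero by definition. The same f is therefore a much larger gap in the endpoint's own unit, change from baseline.

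If 0.5 SD of change were the true gap, the trial would miss it more often than not. A non-significant interaction might then be reported as evidence against a moderate difference. Enrolment is capped at 40, so recruitment could not repair this.

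A second, smaller worry is that the endpoint, hypothesis and analysis sections differ on whether each month, any month or the whole course is being claimed, and that adjustment of the month tests is conditional.

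**Working it through.** **Inputs.** From Section 9.2: two groups, about equal (18 and 18), f = 0.25, alpha 0.05, power 0.95, N = 36, 10% withdrawal. From Sections 3 and 9.1 and the schedule of activities: baseline at Visit 2 plus Visits 3 to 5, so m = 4. Assumed, because not stated: correlation ρ = 0.5 between any two visits, and sphericity.

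**1. Reproducing the stated figure.** The noncentrality is λ = f²·N·m/(1 − ρ) = 0.0625 × 36 × 4/0.5 = 18, with 3 and (36 − 2) × 3 = 102 degrees of freedom. Power is 0.952. At N = 34 it is 0.939, so 36 is the smallest even total reaching 0.95. Then 36/0.90 = 40. Both figures stand.

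**2. f as a gap in change.** Let the gap between groups follow a profile over the four visits with largest value D, in SDs of change. Under equal correlations λ = (n₁n₂/N)·2·D²·SS, where SS is the sum of squared deviations of the profile from its mean. With 18 and 18, (18 × 18/36) × 2 = 18, so λ = 18·D²·SS. Setting λ = 18 gives D = 1/√SS. Setting D = 0.5 gives λ = 4.5·SS.

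| Gap at baseline, months 1, 2, 3 | SS | D at f = 0.25 | λ at 0.5 SD | Power at 0.5 SD, N = 36 |
|---|---|---|---|---|
| 0, 0, 1, 1 | 1.000 | 1.00 | 4.500 | 38.6% |
| 0, 1, 1, 1 | 0.750 | 1.15 | 3.375 | 29.6% |
| 0, 1/3, 2/3, 1 | 0.556 | 1.34 | 2.500 | 22.5% |
| 0, 1/2, 1/2, 1 | 0.500 | 1.41 | 2.250 | 20.6% |

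A profile running from 0 to 1 and staying between them has SS between 0.500 and 1.000, so the first and last rows are the extremes under equal correlations. At N = 40 the power at 0.5 SD is 43, 33, 25 and 23%.

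**3. How far this rests on the assumptions.**

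- *Other inputs that also give 36.* Two visits with ρ of 0.68 to 0.69 need 1.24 SD of change for 95% power. Three visits with ρ of 0.59 to 0.60 need 1.16 or 1.34 SD. Power at 0.5 SD of change is 24 to 31%.
- *Decaying correlation.* With AR(1) correlation of 0.5 to 0.8, a month-3 gap of 0.5 SD of change, and the first three profiles, power is about 29 to 53% uncorrected and 26 to 46% with the Greenhouse-Geisser correction.
- *Which SD.* The correlation cancels only when the gap is in SDs of change. If 0.5 SD means SDs of the scores, power from the linear profile to the late-onset one is 17 to 28% at ρ = 0.3, 36 to 60% at 0.7 and 52 to 80% at 0.8.
- *Keeping f = 0.25 and moving ρ.* Power at N = 36 is 85% at ρ = 0.3, 91% at 0.4 and 98% at 0.6.
- *Reading f = 0.25 as a partial f.* Then λ = 0.0625 × 36 × 3 = 6.75 and power is 55%. Scaled by the error degrees of freedom instead, λ = 0.0625 × 102 = 6.375 and power is 53%. That reading would need 94 to 96 participants for 0.95, so it is not the one behind 36.

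**4. Month-level tests.** In simulation (18 and 18, ρ = 0.5), unadjusted t-tests of change at each month, made only after a significant interaction, give 3.9% false claims when no month differs. When only month 3 differs (f = 0.25), a false claim at month 1 or 2 arises in 8.8% of trials. Holm's adjustment brings these to 2.7% and 4.2%.

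**The case for a change.** The best case for a change is that the label f = 0.25 covers anything from 53 to 95% power at N = 36, depending on an option that Section 9.2 does not state, and that no MIBS-4 SD or earlier difference supports a gap of 1 SD or more. Disclosing the inputs and the detectable gap would cost a few sentences and no patients. It would also guard against over-reading a null result.

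Much of that stands as a comment on reporting. The inputs are unstated, and *medium* is a poor guide to the size of gap involved. It does not show a wrong number. The section names the interaction test and gives f itself, and the stated power follows from an ordinary set of inputs. The half-SD yardstick comes from the one-way comparison, which is not the planned test, and no part of the protocol makes 0.5 SD the difference to be detected. Responders may well differ by 1 SD or more; the documents support neither view.

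Printing a detectable range in Section 9.2 has its own difficulty. Every version depends on a time course and correlation structure that the documents do not supply, so it would exchange one unsupported figure for another.

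On multiplicity, the plan already makes post-hoc tests conditional on a significant result and promises adjustment where needed. The 8.8% case is one where adjustment is needed, so the existing sentence covers it. The choice of method is a SAP detail.

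**Conclusion.** No change is called for. Section 9.2 delivers the power it states for the test and the f it names: 0.952 at 36 evaluable participants, given four visits, equal correlations of 0.5, sphericity and equal groups.

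On those assumptions f = 0.25 is a gap of 1.00 to 1.41 SD of change. A gap of 0.5 SD would be detected in 21 to 39% of trials, and in up to about 53% with decaying correlation and no correction. That is worth knowing when the results are read. At N = 36 the 95% interval for one month's gap has a half-width of t(0.975, 34) × √(2/18) = 0.68 SD of change. Estimates reported with their intervals, as is routine, would show directly what a null interaction leaves open.

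The remaining points are gaps that analysts fill sensibly: the unstated power inputs, the uneven wording of the claim across Sections 3, 9.1 and 9.4.2, and the unnamed adjustment. The analysis section identifies the interaction as the primary test, and the SAP is due before database lock. Filling these gaps alters neither the sample size, the visits nor the primary test. Sizing for 0.5 SD of change over the first three profiles would take 90 to 160 participants even at 80% power, well above the cap of 40 for this single-arm, open-label study.
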